## 6.8 Enrollment and baseline

When a patient signs and dates the Consent Form, he/she is considered a subject enrolled in the study. The date the subject signed the Consent Form and Authorization to Use and Disclose Personal Health Information/Research Authorization must be documented. The following evaluations will be performed after consent, unless previously performed as part of routine clinical evaluations within the specified windows:

### Within 12 months prior to the consent date or between consent date and procedure date

If the subject has a diagnosis of persistent AF, confirm the left atrial volume index is  $\leq 40 \text{ ml/m}^2$  by a trans-thoracic echocardiogram.

A trans-thoracic echocardiogram on file can be used providing it is within the last year from the date of consent, if not, perform a trans-thoracic echocardiogram.

### After consent date but before the procedure date

- Assessment of all factors specified for evaluation under Inclusion Criteria and Exclusion Criteria (Section 5.2).
- Medical history including: assessment of risk factors, NYHA cardiac functional class, systemic history and cardiovascular history, assessment of atrial fibrillation history and symptoms and other arrhythmic episodes
- Physical examination: height, weight, and heart rate.
- Office blood pressure: To assess if the average of 3 office systolic blood pressures measured per guidelines (Appendix G: Blood Pressure Measurement Procedures) is  $> 140 \text{ mmHg}$ .
  - If a subject's average of 3 systolic blood pressures is  $\leq 140 \text{ mmHg}$ , then repeat blood pressure measures (according to Appendix G: Blood Pressure Measurement Procedures) are allowed up to two times over the subsequent 2 weeks. Any subjects with an average office systolic blood pressure  $\leq 140 \text{ mmHg}$  after a total of three attempts will be excluded from the study.
  - For instructions on blood pressure measurement, see Appendix G: Blood Pressure Measurement Procedures.
  - This will be the baseline measurement for statistical comparison and inclusion criteria
- Laboratory testing: Subjects should be instructed to avoid eating or drinking caffeine or alcohol for 10-12 hours prior to lab testing but should drink water normally (avoid other liquids) and take prescribed medications during this time.
  - Serum creatinine (sCr) to calculate eGFR for eligibility criteria and as a factor of baseline kidney function. eGFR should be calculated using the Modification of Diet in Renal Disease (MDRD) Formula:  $eGFR (\text{mL/min}/1.73 \text{ m}^2) = 175 \times (\text{sCr}/88.4) \times 1.154 \times (\text{Age}) - 0.203 \times (0.742 \text{ if female}) \times (1.212 \text{ if of African descent})$  (SI units).
  - Subjects with  $eGFR < 30 \text{ mL/min}/1.73 \text{ m}^2$  will be excluded from the study.

- Spot urine albumin and creatinine to evaluate the albumin to creatinine ratio (UACR) as a factor for baseline kidney function.
  - Blood test: Cystatin C to help detect and monitor acute and chronic kidney dysfunction.
- Confirm the subject has eligible renal anatomy via computerized tomography (CT scan)
  - Perform randomization after eligibility has been confirmed, see Section 6.9.

#### **Performed within 5 days prior to the procedure date**

- Blood or urine test-Serum or urine human chorionic gonadotropin (hCG) Pregnancy test to confirm negative pregnancy status of females of childbearing potential.
- Transesophageal Echocardiogram (TEE)
 

Prior to undergoing an AF ablation procedure, a TEE should be performed in all subjects with atrial fibrillation more than 48 hours in duration or of an unknown duration if adequate systemic anticoagulation has not been maintained for at least 3 weeks prior to the ablation procedure.

Performance of a TEE in subjects who are in sinus rhythm at the time of ablation or subjects with AF who are in AF but have been in AF for 48 hours or less prior to AF ablation may be considered but is not mandatory.

Subjects noted to have left atrial thrombus on TEE will not undergo the procedure and will be exited from the study unless thrombus resolution is confirmed on a repeat TEE.

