- Serious medical condition, which may adversely affect the safety and/or effectiveness of the participant or the trial (e.g., patients with clinically significant peripheral vascular disease, abdominal aortic aneurysm, bleeding disorders such as thrombocytopenia, hemophilia, or significant anemia)

- Pregnant, nursing or planning to be pregnant. [Female participants of childbearing potential must have a negative serum or urine human chorionic gonadotropin (hCG) pregnancy test prior to angiography]
- Known history of drug use or alcohol dependency, lacks the ability to comprehend or follow instructions, or would be unlikely or unable to comply with study follow-up requirements
- Previous organ transplant
- Currently enrolled or plans to participate in a potentially confounding drug or device trial during the course of this study. Co-enrollment in concurrent studies is allowed when documented pre-approval is obtained from the Medtronic study manager.

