#### **6.5 Data collection**

Clinical data is collected at designated time points throughout the study. Data will be collected using an electronic data management system for clinical studies.

Data will be stored in a secure, password-protected database which will be backed up nightly. Data will be reviewed using programmed and manual data checks.

Data queries will be made available to study centers for resolution. Study management reports may be generated by Medtronic to monitor data quality and study progress. At the end of the study, the data will be frozen and retained indefinitely by Medtronic. Data collection requirements are summarized in Table 5.

Table 5: Data collection and study procedure requirements at subject visits

	Enrollment/Baseline	CT Scan	Cryoablation Procedure	Renal Artery Denervation	Reveal LINQ Insertion	Hospital Discharge	1 month	6 month	Every 6 months until study end closure	12 month	Unscheduled	Exit	Repeat cryoablation Procedure (0-90 days), if performed
Informed Consent	x												
Inc/Exc criteria	x	x		x								x	
Medical history	x												

[figure not shown]
	Enrollment/Baseline	CT Scan	Cryoablation Procedure	Renal Artery Denervation	Reveal LINQ Insertion	Hospital Discharge	1 month	6 month	Every 6 months until study end closure/12 month	Unscheduled	Exit	Baseline	Cryoablation	Hospital Discharge	Repeat cryoablation Procedure (0-90 days), if performed
Physical exam	x						x	x	x	x	x	x		x	
Trans-Thoracic Echocardiogram	x (1)														
Review medications	x				x	x	x	x	x	x	x	x	x	x	
Office BP x3	x					x (8)	x (8)	x (8)	x		x		x		
Blood and urine labs: Serum Creatinine (sCr), Spot urine albumin and creatinine and Cystatin C	x				x	x	x			x (2)					
Review of symptoms	x						x	x	x	x					
Randomization	x														
Pregnancy test	x (3)														
Transesophageal Echocardiogram (TEE) (3)		x (4)													
Renal angiogram for Treatment group only			x												
Procedure information		x	x	x	x								x		
CareLink in-office interrogation (5)					x (6)		x	x	x	x					
CareLink manual home transmission									x (5)		x				
Renal Artery Imaging-Duplex Ultrasound								x (7)							
Adverse Events, Reveal LINQ System Modification, Death, Study Deviation, Device Deficiencies															As they occur

- For subjects with persistent AF, perform during the 12 month interval preceding the Consent Date, or between Consent Date and Procedure Date.
- Optional, if performed.
- Perform within 5 days prior to the Procedure.

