#### **6.9 Randomization**

Randomization schedules will be prepared for each site using a random permuted block design stratified by center and AF diagnosis. The schedules will allocate subjects in a 1:1 ratio to the treatment or control arm.

Each center will receive a set of sequentially numbered envelopes labeled specifically for that center that is labeled with one randomization code per envelope. After a CT scan has been performed and confirmed that the renal anatomy meets eligibility requirements, the subject will be randomized.

The next sequential envelope labeled with a randomization code will be used. The envelope number will be recorded for each randomized subject and communicated to Medtronic. The sequence of subject randomization will be checked to ensure it matches the sequence of envelope numbers.

Randomization assignments are the following:

- Treatment:
  - Perform the pulmonary vein isolation procedure, renal angiogram, renal artery denervation procedure and the Reveal LINQ insertion.
- Control:

- Perform the pulmonary vein isolation procedure and the Reveal LINQ insertion. Do NOT perform renal denervation.

Enrolled subjects who were not randomized should be exited. See Section 9.2.2 if the subject has an ongoing adverse event.

Subjects and center personnel will be blinded to the randomization assignment until after the pulmonary vein isolation procedure.

Crossing over to the Treatment group once assigned to the Control group is not allowed at any point during the study.

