### 6.12 Renal angiography

Perform renal angiography if randomized to Treatment, following the pulmonary vein isolation procedure.

Subjects should be prepped for a renal angiography according to standard procedures. For subjects with chronic kidney disease and/or risk factors for contrast-induced nephropathy (CIN), the hospital's standard-of-care protocol for CIN prevention should be utilized.

An aortogram and selective renal angiography will be performed to confirm renal artery anatomy. Anatomic eligibility is defined as each kidney having at least one renal artery  $\geq 3$ mm and  $\leq 8$ mm in diameter and minimum treatable length per the Symplicity Spyral Catheter Instructions for Use, without significant stenosis or other abnormality. *NOTE: All renal arteries with  $\geq 3$  mm and  $\leq 8$ mm diameter with minimum treatable length per the Symplicity Spyral Catheter Instructions for Use shall be*

*treated, including dual renal arteries meeting these morphologic criteria.*

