There are additional risks that could possibly be associated with the tests and procedures performed for this study. These potential risks are described below.

There are risks related to the blood tests required for the trial [e.g., excessive bleeding, fainting or light headedness, hematoma (bruising), infection, or the requirement of multiple punctures to locate a vein to draw the sample].

The cryoablation and renal artery denervation involve exposure to a small amount of radiation as part of the fluoroscopy procedure. Possible risks associated with this are:

- Increased risk of cancer and damage to the fetus of pregnant women.
- Increased radiation exposure time if an additional ablation procedure is necessary.
- Radiation injury resulting in skin inflammation and redness.

There are risks of undergoing CT scan, Renal Angiography and chest x-rays. These include: medication patches that can cause a skin burn and allergic reaction to the contrast material (if used) and exposure to radiation.

There is a possibility of risks to an unborn child. These risks are unknown. Women who are pregnant or expect to become pregnant during the course of the study are excluded from participating.

This study may involve unknown or unforeseen side effects or complications other than those mentioned above. If the above complications occur, they may lead to repeat or prolonged hospitalization, repeat procedures, emergency surgery, other emergency procedures or in rare cases, death.

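### The only scheduled pregnancy test falls in the last 5 days before the procedure, so the study CT can expose an unrecognized pregnancy before any test is done

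*Protocol*

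**What the plan says.** Three places in the protocol set the timing of the pregnancy test.

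- **Section 6.8**, in the block for the 5 days before the procedure, asks for a serum or urine hCG "Pregnancy test to confirm negative pregnancy status of females of childbearing potential".
- **Table 5 (Section 6.5)** has a single mark for the test. Its note reads "Perform within 5 days prior to the Procedure".
- **Section 5.2.2** lists pregnancy as an exclusion and asks for a negative "pregnancy test prior to angiography". The SAP repeats this criterion in its own Section 5.2.2.

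The CT is timed separately. Section 6.8 puts confirmation of renal anatomy by CT in the block that runs from consent to the procedure date. That block also lists blood and urine tests of kidney function, but no hCG. Section 6.9 then says: "After a CT scan has been performed and confirmed that the renal anatomy meets eligibility requirements, the subject will be randomized". No maximum interval from CT to procedure is stated. Angiography comes much later: "Perform renal angiography if randomized to Treatment, following the pulmonary vein isolation procedure".

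**The concern.** The test is tied to the procedure, and in the exclusion criterion to angiography, but the first study-driven radiation exposure is the CT. The protocol recognizes the hazard. Section 10 says "There are risks of undergoing CT scan, Renal Angiography and chest x-rays" and names radiation among them. It then states "There is a possibility of risks to an unborn child", and the protection it offers is that pregnant women are excluded.

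For a pregnancy that neither the woman nor the site knows about, exclusion works only if a test finds it before the exposure. As written, a site can follow the plan exactly, scan an unknowingly pregnant woman for study purposes, and learn of the pregnancy afterwards. The stake is an avoidable fetal exposure.

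**Working it through.** The plan states no figure to reproduce. The check sets the timings side by side, with the procedure as day 0.

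| Step | Allowed timing | Source |
|---|---|---|
| Review of eligibility criteria | After consent, before day 0; no hCG specified | Section 6.8 |
| Study CT of renal anatomy | Any date after consent and before day 0 | Section 6.8 |
| Randomization | After the CT confirms eligible anatomy | Sections 6.8, 6.9 |
| hCG test | Day −5 to day 0 | Section 6.8; Table 5 note |
| Negative hCG as an eligibility condition | Before angiography | Section 5.2.2 |
| Angiography | Day 0, after pulmonary vein isolation, Treatment arm only | Section 6.12 |

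**Order of CT and test.** The test window opens on day −5.

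- CT on day −6 or earlier: a test done in the window always comes after the CT.
- CT on day −5 or later: the test may come first, but nothing requires it.

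Because the CT-to-procedure interval has no upper limit, the CT can precede the test by any length of time.

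**Women who fail on the CT.** Section 6.9 exits enrolled subjects who are not randomized. A woman with ineligible anatomy has no procedure date, so the 5-day window never opens for her. She can have a study CT with no scheduled pregnancy test. Section 1.2 expects a fair number of screening failures and gives renal anatomy as one reason.

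**Earlier results.** Section 6.8 accepts evaluations from routine care if they fall in the specified windows. For the hCG test that window is still 5 days before the procedure, so this adds no test before the CT. A CT already done in routine care is not a study exposure and is outside this point.

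**Column position in Table 5.** The test mark stands under Enrollment/Baseline, to the left of the CT column. Its note fixes the window before the procedure, so the column does not place the test before the CT.

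**Reach of a change.** Appendix I records 100 subjects enrolled at version 18.0, and Section 1.2 allows up to 245:

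245 − 100 = 145

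This is a ceiling. It covers both sexes and is before screening failures. The 245 is itself only an upper limit, and enrollment may stop early at an interim analysis.

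**Effect on the analysis.** A positive test after randomization would lead to exit before pulmonary vein isolation. Such a subject does not count toward the 70 (protocol Section 12.1; SAP Section 6), and an unrevealed envelope may go back to the pool (SAP Section 5.3). The planned sample size and power are unaffected.

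**The case against.** The strongest reply is that this is a missing instruction in a plan that already controls for pregnancy. Pregnancy is an exclusion reviewed after consent, and Table 5 as extracted also marks the eligibility criteria at the CT step. Nothing forbids an earlier test. The Section 5.2.2 condition is a deadline that a screening test would meet. Consent templates are distributed separately, and radiology departments may check pregnancy status themselves. Section 10 attaches its specific phrase on fetal damage to procedural fluoroscopy, and its sentence on the unborn child is general and says the risks are unknown. With drug-refractory atrial fibrillation and uncontrolled hypertension as entry criteria, few women of childbearing potential may be enrolled. Any protocol change also needs sponsor, regulator and ethics approval at each center (Section 4).

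Part of this stands. The size of the fetal risk from one CT cannot be taken from these documents, nor can the number of women affected. The approvals are a real cost.

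The gap remains. A criteria review that specifies no hCG test cannot be relied on to find a pregnancy nobody knows about. Permission to test early is not a requirement to do so. Local practice and unseen consent text are not in the plan, and Section 5.3 relies on procedures being standardized across centers. Women of childbearing potential are eligible (ages 18 to 80, Section 5.2.1), and the plan specifies a test for them.

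**Conclusion.** The concern holds. The current protocol allows a study-required CT before the only scheduled pregnancy test, makes that order certain for any study CT 6 or more days before the procedure, and may leave women who fail on the CT untested. It should be corrected, as a matter of subject safety only.

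The number affected is unknown: an unstated subset of at most 145 further enrollments. The conclusion assumes that the CT is done for the study, that the pregnancy is unrecognized, and that the site does no test beyond what the protocol asks.

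**What to change.** Amend protocol Sections 5.2.2, 6.8 and 6.9 and Table 5 to require a negative serum or urine hCG test in women of childbearing potential before any CT performed for the study, and before randomization where a routine-care CT is used. Keep the test within 5 days before the procedure when the earlier result falls outside that window. Give the new requirement its own note in Table 5, because the existing note also governs the transesophageal echocardiogram. Align the copy of the criterion in SAP Section 5.2.2.

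The cost is protocol wording and at most one extra hCG test, of a kind already in the plan, per woman of childbearing potential. The approvals required at up to 15 centers (12 + 3) can be obtained as part of another amendment.

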#### **6.9 Randomization**

Randomization schedules will be prepared for each site using a random permuted block design stratified by center and AF diagnosis. The schedules will allocate subjects in a 1:1 ratio to the treatment or control arm.

Each center will receive a set of sequentially numbered envelopes labeled specifically for that center that is labeled with one randomization code per envelope. After a CT scan has been performed and confirmed that the renal anatomy meets eligibility requirements, the subject will be randomized.

The next sequential envelope labeled with a randomization code will be used. The envelope number will be recorded for each randomized subject and communicated to Medtronic. The sequence of subject randomization will be checked to ensure it matches the sequence of envelope numbers.

Randomization assignments are the following:

- Treatment:
  - Perform the pulmonary vein isolation procedure, renal angiogram, renal artery denervation procedure and the Reveal LINQ insertion.
- Control:

- Perform the pulmonary vein isolation procedure and the Reveal LINQ insertion. Do NOT perform renal denervation.

Enrolled subjects who were not randomized should be exited. See Section 9.2.2 if the subject has an ongoing adverse event.

Subjects and center personnel will be blinded to the randomization assignment until after the pulmonary vein isolation procedure.

Crossing over to the Treatment group once assigned to the Control group is not allowed at any point during the study.

## 6.10 Pulmonary vein isolation procedure

Perform the pulmonary vein isolation procedure first using Arctic Front Advance/Arctic Front Advance Pro. Investigator is to perform the procedure according to the procedural steps in this protocol and the Instructions for Use for the Arctic Front Advance/Arctic Front Advance Pro Cardiac Cryoablation System. Appropriate systemic anticoagulation and sedation should be attained at the investigators discretion according to their institutions pre- established procedures/guidelines at the time of the procedure. Current recommendations for anticoagulation are found in the 2012 Expert Consensus Statement on the Ablation of atrial fibrillation.

### 6.10.1 Diaphragm Movement

- Phrenic nerve pacing or other phrenic nerve monitoring technique must be done for each cryoapplication, specifically those cryoapplications surrounding the RS and RI pulmonary veins
- Prior to the first cryoablation application, the Investigator will make a fluoroscopic recording of inspiratory and expiratory movement of the diaphragm
- After the last cryoablation application, the investigator will make a fluoroscopic recording of the inspiratory and expiratory movement of the diaphragm

### 6.10.2 Balloon Pulmonary Vein (PV) Cryoablation

- Every effort consistent with subject welfare will be made to treat all PVs or their anomalous equivalents.
- The Arctic Front Advance/Arctic Front Advance Pro Cardiac Cryoablation Catheter will then be advanced into the LA and inflated. Once inflated, the catheter will be tracked over the wire and positioned at the entrance of the PV.
- Assess the positioning, contact and occlusion of the PV by the catheter's balloon by ultrasound imaging, injection of contrast material or other technique. Reposition as needed.
- After one or more cryoapplications, each pulmonary vein should be minimally assessed for entrance block and, where assessable, exit block to demonstrate the cryoablation procedure endpoint of electrical isolation of the four major PVs.

### 6.10.3 Gap or Touch Up Ablation

At the Investigator's discretion, a focal cryocatheter or a radio frequency catheter may be performed to complete electrical isolation of one or more PVs.

#### 6.10.4 Other Ablations

Subjects may have other cardiac rhythm abnormalities requiring treatment detected during the ablation procedure. This may include right/left atrial flutter or atrial fibrillation triggers. Treatment of such abnormalities is at the Investigator's discretion. Such ablation will be fully documented in the relevant CRF.

#### 6.10.5 Procedure Documentation

During the procedure the investigator will document the following:

- a. Catheter used for each ablation (i.e. Arctic Front Advance/Arctic Front Advance Pro, Freezor MAX or radiofrequency)
- b. Temperature for each application
- c. Duration of each application
- d. Vein location for each application (e.g. right superior pulmonary vein)
- e. Use of phrenic nerve pacing or other phrenic nerve monitoring technique for each application, specifically those applications surrounding the RS and RI pulmonary veins
- f. Demonstrated electrical block
- g. Adjunctive mapping or visualization devices, sedation type, procedure information, fluoroscopy time, contrast dye amount and concentration will be collected.

